Assessment of local pain		X	X	X	X	X	X	X	X	X	X	X	X	X	X	X	X	X
Assessment of local edema		X	X	X	X	X	X	X	X	X	X	X	X	X	X	X	X	X
Assessment of local erythema		X	X	X	X	X	X	X	X	X	X	X	X	X	X	X	X	X
Dispensing of Wound dressing material*		X	X	X	X	X	X	X	X	X	X	X	X	X	X	X	X	

^a Medical and ulcer history will also include foot specific history such as location and duration of the selected ulcer and other medical conditions of the Subject. Events occurring prior to application of first dose of IP will be recorded as medical history and events occurring after the application of first dose of IP will be recorded as adverse events

^b Laboratory tests will be performed at Screening Visit V1, V6, V10, V14 or EOT and during follow-up only at V18 or EOS and will include:

- Hematology parameters: CBC: WBC, RBC, Hematocrit, Hemoglobin, MCV, MCH, MCHC, RDW, Platelet Count, Mean Platelet Volume.
- Biochemistry parameters: Glucose, Calcium, Albumin, Total Protein, Sodium, Potassium, CO₂, Chloride, BUN, eGFR, ALP, ALT, AST, Bilirubin.
- HbA_{1c}
- Urine pregnancy test will be done in women of child bearing potential at Screening Visit V1, V6, V10, V14 or EOT and during follow-up only at V16/FU2 throughout the Study

^c ECG will be done at Screening Visit V1, V6, V10, and V14 or EOT and during follow-up only at V15/FU1

^d Study Diary review will be done by unblinded Investigator during Study Nurse visit to the site

^e Subject Diary review will be done by blinded Investigator for all subjects in follow up Phase

^f Ankle Brachial Index and 5.0 SW monofilament test will be performed at the Screening Visit V1

^g X-ray of the foot under Study will be performed at the Screening Visit and further at the Investigator's discretion to rule out osteomyelitis.

^h The Investigator will re-assess Subject eligibility at Baseline Visit V2, with emphasis on reduction of ulcer size since Screening Visit V1. If a potential Target Ulcer has decreased ≥30% between the Screening and Baseline visits, then this potential Target Ulcer cannot be designated as Target Ulcer. If none of the potential Target Ulcer(s) meet eligibility criteria at the Baseline V2, Subject will be considered as screen failure and exit the Study without further evaluation. If the Subject has more than one qualifying ulcer, the ulcer designated as the Target Ulcer should be the ulcer on the plantar region which is older, deeper and with a larger area

ⁱ Re-dispensing of IP may occur as and when required during Treatment Phase

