^j Subject Education and training on Diabetes management and use of off-loading device will be done as and when required

^k The AE reporting will begin from the application of the first dose of the IP from the Baseline Visit

^l Debridement of ulcer as and when necessary during site visit

^m Nutritional information should be provided to Subject as and when necessary

ⁿ Photographs of both the legs will be taken from various angles to ensure that there are no more than three ulcers on both the legs

^o In case the ulcer/wound closes within 12-weeks of Treatment Phase, the Subject will immediately enter the 12-weeks of Follow-Up Phase. In case of the Subject, whose Target Ulcer reopens during 12-weeks of Treatment Phase (within 84 days from Baseline) which is prior to the confirmation of Target Ulcer closure, the Subject would be given the treatment to complete 12-week of Treatment Phase

^p During Follow-Up Phase, if the Target Ulcer has reopened after confirmation of its closure, the Subject will still be continued with the Follow-up assessment.

^q This window period is from the Screening Visit

^r EOT is at week 12 visit or any visit on which first observation of Target Ulcer closure has happened or treatment is Stopped

^s EOS is at week 24 visit or any visit on which the Subject exits the Study

^t Window period of ±3 days will be allowed for each Treatment visit as well as FU1 and FU2 visits and window period of ±5 will be allowed for FU3 and FU4

Note: *Dispensing of Wound dressing material will be provided as long as required

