4.4 END OF STUDY DEFINITION

A participant is considered to have completed the Study if he or she has completed all phases of the study including the last visit or the last scheduled procedure shown in the Schedule of Activities (SoA), [Section 1.3](#). The end of the study is defined as completion of the last visit or procedure shown in the SoA in the trial. In addition, if Subject is discontinued or withdrawn from the Study, the last recorded visit of such Subject shall be considered as the End of Study.

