7 STUDY INTERVENTION DISCONTINUATION AND PARTICIPANT DISCONTINUATION/WITHDRAWAL

7.1 DISCONTINUATION OF STUDY INTERVENTION

The subjects that report Osteomyelitis, cellulitis or SAE/AE where study intervention cannot be given, should be discontinued. For all discontinued Subjects, maximum possible and relevant Study information shall be gathered and be described in the source. This information can be gathered at Site visit or telephonically. If the discontinuation happens during the Treatment /Follow up Phase, the last visit prior to discontinuation will be treated as EOT/EOS visit and corresponding CRF will be completed by the Investigator.

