7.2 PARTICIPANT DISCONTINUATION/WITHDRAWAL FROM THE STUDY

Participants are free to withdraw from participation in the Study at any time. If the withdrawal happens during the Treatment /Follow up Phase, the last visit prior to withdrawal will be treated as EOT/EOS visit and corresponding CRF will be completed by the Investigator.

Subjects who sign the informed consent form (ICF) and are randomized but do not receive the study intervention will not be replaced and will not be part of ITT Population.

Subjects who sign the ICF, and are randomized and receive the study intervention, and subsequently withdraw, or are withdrawn or discontinued from the study, will not be replaced and yet be part of ITT Population.

Subjects must be discontinued from the Study after randomization if any of the following events occur (Stopping or Discontinuation Rules for Individual Subjects):

1. A Subject withdraws consent
2. Investigator recommends that the Subject should discontinue the participation in the Study
3. Subject misses two consecutive Weekly Visits during Treatment Phase
4. If the Target Ulcer and the adjoining wound merge together and if the Investigator opines that following the Target Ulcer is difficult. A detailed note by the Investigator will be recorded in the e-CRF outlining reasons for such merger in line with the preceding measurement of Target Ulcer
5. If Subject requires hospitalization for more than two consecutive weeks during the Study
6. The Subjects with treatment compliance of less than 80% or more than 120% during the week, will be considered treatment non-compliant for that week. If such non-compliance is observed for more than three weeks, and if the blinded Investigator opines that it may affect the outcome of the Study, then the Subject shall be considered non-compliant for the Study and shall be discontinued from the Study
7. If the blinding of a Subject is compromised
8. Any form of major protocol violation
9. The Target Ulcer increases in size (more than 30%) for two consecutive weeks or requires deep, surgical debridement for more than two occasions during the Treatment Phase to address Target Ulcer deterioration
10. The Target Ulcer becomes infected requiring topical antimicrobial treatment
11. If Subject develops osteomyelitis or cellulitis during the Study on the foot having the Target Ulcer
12. If female Subject becomes pregnant, during the study
13. If Subject misses 6 consecutive dressings

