In the event of a Subject withdrawal or discontinuation from the Study, the following information must be recorded in the e-CRF

- Date of withdrawal
- Reason for withdrawal
- Last treatment date

In the event of withdrawal or discontinuation, the Subject will be requested to cooperate for the following:

- a. Recording AEs that may occur post withdrawal/discontinuation till End of Study
- b. Follow-up on all SAEs or other AEs that may have occurred prior to withdrawal/discontinuation and are considered to be related to the Study IP, until resolved or assessed to be chronic or stable by the Investigator. The details would be documented in the Subject's medical records

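### The protocol gives conflicting definitions of EOT/EOS for subjects who stop early, and the rule in Sections 7.1 and 7.2, read literally, places EOT at a visit where the exit safety tests were usually not scheduled

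*Combined protocol and SAP*

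**What the plan says.** The protocol defines EOT and EOS for early stoppers in several places.

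- **Section 1.3, footnote r:** "EOT is at week 12 visit or any visit on which first observation of Target Ulcer closure has happened or treatment is Stopped".
- **Section 1.3, footnote s:** "EOS is at week 24 visit or any visit on which the Subject exits the Study".
- **Section 7.1 (discontinuation):** "the last visit prior to discontinuation will be treated as EOT/EOS visit and corresponding CRF will be completed by the Investigator".
- **Section 7.2 (withdrawal):** "the last visit prior to withdrawal will be treated as EOT/EOS visit".
- **Section 4.4 (discontinued or withdrawn):** "the last recorded visit of such Subject shall be considered as the End of Study".
- **Section 7.3 (lost to follow-up):** the last scheduled visit is used.

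The tests hang on these labels. Footnote b states: "Laboratory tests will be performed at Screening Visit V1, V6, V10, V14 or EOT and during follow-up only at V18 or EOS". Section 8.1 gives the same visits for the physical examination. ECG is due at V1, V6, V10, V14 or EOT, and FU1. HbA1c after screening is due only at V14 or EOT and at V18 or EOS.

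Section 7.1 also asks sites to gather as much relevant information as possible on discontinued subjects, at a site visit or by telephone, but names no tests. Only the pregnancy rule (Section 8.2.11) requires the End of Study procedures on stopping.

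After withdrawal or discontinuation, Section 7.2 asks subjects to cooperate with: "Recording AEs that may occur post withdrawal/discontinuation till End of Study".

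**The concern.** The footnotes attach the EOT/EOS assessments to the visit at which the subject stops. Sections 7.1 and 7.2 attach the label to a visit before that and require only that its CRF be completed. A visit already past cannot supply tests that were not scheduled then. The subjects concerned include those named in Section 7.1, who stop for osteomyelitis, cellulitis or an adverse event that prevents further treatment.

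Two things are at stake. First, laboratory, ECG and physical examination results at exit may be missing, or may predate the event, in subjects for whom they are most informative. Sites that follow the footnotes and sites that follow Section 7.1 would also collect different data under the same label. Second, the post-withdrawal adverse event request runs until End of Study. If End of Study is a visit already past, the request covers no time at all.

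**Working it through.** The protocol gives no figure for this, so the check is a count of visits against the Schedule of Activities and Section 8.1.

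**Stopping during treatment.** If the labelled EOT is the last ordinary visit before stopping, it is one of V2 to V13, which is 12 visits.

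| Assessment | Scheduled at, within V2–V13 | Possible EOT visits without it |
|---|---|---|
| Laboratory tests | V6, V10 | 10/12 = 83% |
| ECG | V6, V10 | 10/12 = 83% |
| Physical examination | V6, V10 | 10/12 = 83% |
| Detailed foot examination | V2, V6, V10 | 9/12 = 75% |
| HbA1c | none | 12/12 = 100% |
| Vital signs, Target Ulcer measurement and local examination | every visit | 0/12 |

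If the labelled visit is V2 to V5 (4/12 = 33%), the subject has no scheduled laboratory test or ECG after screening. As an example, a subject who is hospitalised between V8 and V9 and discontinued has V8 (week 6) as EOT. The latest scheduled laboratory tests and ECG are then those of V6 (week 4).

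**Leaving in follow-up.** The prior visit is one of V14, FU1, FU2 or FU3. Laboratory tests, HbA1c and physical examination are scheduled at V14 only, so 3 of 4 (75%) lack them. These subjects have already had their EOT tests, and no ECG is due at EOS.

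**Possible numbers.** The planned drop-out in Groups 1 and 2 is 20% of 300 = 60. The timing of drop-out is not stated. Assume that a fraction f stops during treatment, spread evenly over the 12 visits. The share of all early stoppers whose labelled EOT has no laboratory tests is then f × 10/12:

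- f = 1: 83%, or 60 × 10/12 = 50 subjects
- f = 0.75: 63%
- f = 0.60: 50%
- f = 0.50: 42%, or 60 × 0.50 × 10/12 = 25 subjects

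The share passes one half only when f exceeds 0.5 ÷ (10/12) = 0.60. With f = 1, those with no post-baseline laboratory test or ECG number 60 × 4/12 = 20.

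**Lost to follow-up.** Section 7.3 defines these subjects partly by failure to return for two consecutive scheduled visits, then labels the last scheduled visit as EOT/EOS. That can be a visit nobody attended.

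**The case against.** The best defence is that Section 7.1 cancels no test. The last visit before discontinuation can be read as the visit where the decision is taken, and footnote r would then bring the EOT assessments with it. Ulcer enlargement, merging ulcers, infection and osteomyelitis would often be found at a site visit. Section 7.1 asks for all obtainable information, and Section 8 asks for phase-relevant assessments at unscheduled visits. Section 8.2.6 attempts 12 weeks of follow-up for adverse events present at early withdrawal, and Section 7.2 follows earlier treatment-related events until they resolve or stabilise.

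Much of this stands, and it limits the size of the problem. It does not remove the conflict. The wording is prior to, and several stopping reasons arise away from a visit: withdrawn consent, missed visits, prolonged hospital stay and missed dressings. Telephone contact cannot yield a blood sample or an ECG. Section 8.2.6 covers events already present, so new events after withdrawal still have no workable end date. If both readings are open, sites will differ.

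A reader might go further and infer that the safety conclusion rests mainly on subjects who completed treatment or whose ulcer closed. The documents do not support that. The safety endpoint for Galnobax is the proportion of subjects with treatment-emergent adverse events. Subjects who stop early stay in the ITT population (Section 7.2), and adverse events are assessed at every visit from first dose. The laboratory tables in Section 9.4.4.2 are by relevant visit and are not confined to EOT.

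**Conclusion.** The conflict between Sections 4.4, 7.1, 7.2 and 7.3 and footnotes r and s is real and needs correcting. Under the literal rule in Sections 7.1 and 7.2, a treatment-phase stopper's EOT visit has no scheduled laboratory tests, ECG or physical examination unless it happens to be V6 or V10, and never has HbA1c. These counts follow directly from the schedule.

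The number of subjects does not. About 50 of 60 is an upper illustration that assumes every drop-out occurs on treatment and evenly by visit. Some of those subjects, such as those lost to follow-up or refusing further contact, could not supply exit tests under any wording.

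Two stronger inferences fail. It is not established that most early stoppers lack EOT tests, since that needs more than 60% of them to stop during treatment on the even-spread assumption. Nor is it true that nobody leaving in follow-up would have EOS laboratory results, because V14 carries them.

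Severity is moderate. Exit laboratory tests, ECG, physical examination and post-withdrawal adverse events may be incomplete. The primary test, alpha and power are unaffected.

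**What to change.** Reconcile Sections 4.4, 7.1, 7.2 and 7.3 with footnotes r and s so that one definition applies:

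- EOT/EOS is the visit at which treatment is stopped or the subject exits.
- The assessments already in the EOT/EOS column of the Schedule of Activities are done at that visit where the subject can attend.
- Where the subject cannot attend, EOT/EOS is recorded as not done, and no earlier or unattended visit is relabelled.
- Post-withdrawal adverse event recording in Section 7.2 gets a defined end, for example the 12 weeks already used in Section 8.2.6.

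This changes only where data are collected and how a visit is labelled, not when or why treatment is stopped. It adds no test beyond the existing column. The cost is a wording change in a few sections and the effort of arranging some exit visits.

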7.2 PARTICIPANT DISCONTINUATION/WITHDRAWAL FROM THE STUDY

Participants are free to withdraw from participation in the Study at any time. If the withdrawal happens during the Treatment /Follow up Phase, the last visit prior to withdrawal will be treated as EOT/EOS visit and corresponding CRF will be completed by the Investigator.

Subjects who sign the informed consent form (ICF) and are randomized but do not receive the study intervention will not be replaced and will not be part of ITT Population.

Subjects who sign the ICF, and are randomized and receive the study intervention, and subsequently withdraw, or are withdrawn or discontinued from the study, will not be replaced and yet be part of ITT Population.

Subjects must be discontinued from the Study after randomization if any of the following events occur (Stopping or Discontinuation Rules for Individual Subjects):

1. A Subject withdraws consent
2. Investigator recommends that the Subject should discontinue the participation in the Study
3. Subject misses two consecutive Weekly Visits during Treatment Phase
4. If the Target Ulcer and the adjoining wound merge together and if the Investigator opines that following the Target Ulcer is difficult. A detailed note by the Investigator will be recorded in the e-CRF outlining reasons for such merger in line with the preceding measurement of Target Ulcer
5. If Subject requires hospitalization for more than two consecutive weeks during the Study
6. The Subjects with treatment compliance of less than 80% or more than 120% during the week, will be considered treatment non-compliant for that week. If such non-compliance is observed for more than three weeks, and if the blinded Investigator opines that it may affect the outcome of the Study, then the Subject shall be considered non-compliant for the Study and shall be discontinued from the Study
7. If the blinding of a Subject is compromised
8. Any form of major protocol violation
9. The Target Ulcer increases in size (more than 30%) for two consecutive weeks or requires deep, surgical debridement for more than two occasions during the Treatment Phase to address Target Ulcer deterioration
10. The Target Ulcer becomes infected requiring topical antimicrobial treatment
11. If Subject develops osteomyelitis or cellulitis during the Study on the foot having the Target Ulcer
12. If female Subject becomes pregnant, during the study
13. If Subject misses 6 consecutive dressings

In the event of a Subject withdrawal or discontinuation from the Study, the following information must be recorded in the e-CRF

- Date of withdrawal
- Reason for withdrawal
- Last treatment date

In the event of withdrawal or discontinuation, the Subject will be requested to cooperate for the following:

- a. Recording AEs that may occur post withdrawal/discontinuation till End of Study
- b. Follow-up on all SAEs or other AEs that may have occurred prior to withdrawal/discontinuation and are considered to be related to the Study IP, until resolved or assessed to be chronic or stable by the Investigator. The details would be documented in the Subject's medical records

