6.3 MEASURES TO MINIMIZE BIAS: RANDOMIZATION AND BLINDING

This is a double-blind study wherein the Investigator, the Sponsor, the Subject, the CRO and the Study Nurse Coordinator will be kept blinded to the randomization throughout the Study. There will be one unblinded Investigator per site who will administer the treatment during each treatment visit of the Subject as well as dispense the IP to the Study Nurse and the SoC material to the Subject. The Study Nurse who will administer treatment to the Subject (twice daily during Treatment Phase) will be unblinded. However, the unblinded Investigator and Study Nurse will still remain blinded to whether the Study drug applied is Galnobax® or Vehicle gel. The blinding of the Subject will be ensured by the Study Nurse by using shield while treating the Target Ulcer.

In case the Subject is staying far from the site (i.e. 40 km or more from the site) and/or Nurse is unable to visit every week to the site for treatment compliance check, following procedure will be followed for IP transport and compliance check: IP will be issued to the study Nurse at the time of the randomization visit along with study diary in an aluminum box having a lock. One key of this lock will be with the study Nurse and other with the unblinded CRC at the site. At the time of weekly site visit of the Subject, study Nurse will keep used IP tubes and Study diary in this box which will be locked and sent to the site with the Subject. Site unblinded CRC will take aluminum box from the subject and will check IP compliance as well as study diary. The IP will be reissued to the nurse after weighing the tubes and new study diary will also be issued (through which new dose of the subject will be conveyed to the Nurse). These materials will be kept in the aluminum box which will be locked and given to the Subject for handing over it to the study Nurse. This process will continue during all treatment visits.

While the IP compliance will be verified by the unblinded Investigator, the Target Ulcer Closure will be decided and confirmed by the blinded Investigator, thus mitigating any bias.

Unblinding will be done only if necessary for the welfare of the Subject or in the case of emergency suspected to be IP related. If such emergency is clearly not IP-related in the opinion of the Investigator, the Subject management can be done without the need of unblinding. Standard norms and procedures for unblinding will be followed.

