9.2 SAMPLE SIZE DETERMINATION

This Study will have FAS Population (Efficacy Evaluable Population) of minimum of 240 Subjects (minimum of 120 each in Group 1 and Group 2). To ensure this and assuming 20% drop out rate, the population of two groups would be up to 300 Subjects. For safety analysis of Vehicle of Galnobax®, maximum of 50 Subjects will be recruited in Vehicle plus SoC group. Thus, overall population of maximum of 350 Subjects will be recruited in the Study.

Sample Size Determination and Rationale:

The sample size calculation has two components. One is based on statistical power and the other is based on clinical judgment.

The sample size calculation is based on the primary endpoint for the Study that is proportion of Subjects achieving complete closure of Target Ulcer within 12-week Treatment Phase, as determined by blinded Investigator's assessment.

The sample size is obtained based on the assumption that there will be a clinically meaningful difference of 21%, (i.e., 39% of SoC vs 60% of Galnobax®-treated achieved complete closure of Target Ulcer, odds ratio of 0.65). This assumption is based on the following:

- a. Literature reports from various DFU trials showed that average percent wounds closed using SoC treatment is 24% globally.^{5 27} However, percent wounds closed using SoC treatment in recently completed DFU trial in India is reported to be 37.8%.²⁸ In view of this, it is assumed that 39% wounds may close in the SoC group.
- b. In Phase 1/2 study of Galnobax®, 60% wounds closed within 12-week of Galnobax® treatment. Furthermore, 67% wounds were closed in Galnobax® arm for wounds with wound age > 6 weeks. In view of this, the inclusion criterion is revised to include Subjects with wounds of at least 6 weeks (which was 4 weeks in Phase 1/2 study) and it is assumed that 60% wounds may close in the Galnobax® treatment group.

To meet the Type I error rate of 0.05 (95% confidence interval), 2-sided analysis and 90% power, 120 Efficacy Evaluable Subjects in Group 1 and Group 2 will be required for making the FAS Population in the Study as 240. To accommodate the potential drop outs rate of 20%, a total of 300 Subjects will be randomized in these Groups to ensure more than 90% power for the primary endpoint analysis (i.e., proportion of Subjects achieving Target Ulcer Closure within 12-week Treatment Phase).

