The safety evaluation of Vehicle of Galnobax® will be done by recruiting population of 50 Subjects in the Vehicle plus SoC group. As there is not hypothesis testing or statistical comparison proposed for this arm, this population might not be statistically significant, but would enough to give reasonable estimate of safety for Vehicle of Galnobax®.

9.2.1 RANDOMIZATION AND STRATIFICATION OF STUDY POPULATION:

Prior to randomization, Subjects will be stratified by location of Target Ulcer (planter or non-planter), and the Target Ulcer size ($<5\text{ cm}^2$ or $\geq 5\text{ cm}^2$). The randomization will be done at the ratio of 3:3:1 in one of the following groups, using an IWRS:

- Galnobax® 14% plus SoC or
- SoC or
- Vehicle plus SoC

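### Section 7.2 ends study follow-up, not only treatment, for events that leave Target Ulcer closure assessable, so later closure is not collected and the comparison may be biased

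*Combined protocol and SAP*

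**What the plan says.** Section 7.2 introduces its individual stopping rules with "Subjects must be discontinued from the Study after randomization if any of the following events occur". The wording covers participation in the Study, not only study treatment. Five of the thirteen events do not in themselves make the ulcer unassessable: two consecutive missed weekly visits (rule 3), repeated non-compliance judged by the blinded Investigator to affect outcome (rule 6), "If the blinding of a Subject is compromised" (rule 7), any major violation (rule 8) and six consecutive missed dressings (rule 13).

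What follows removal is set out in several places:

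- Sections 7.1 and 7.2 treat the last visit before discontinuation or withdrawal as EOT/EOS. Note s to the Schedule of Activities (Section 1.3) and Section 4.4 likewise make the exit or last recorded visit the End of Study.
- Section 7.2 then asks the subject to cooperate with "Recording AEs that may occur post withdrawal/discontinuation till End of Study" and with follow-up of earlier SAEs and related AEs. Closure is not on that list.
- The Definitions require closure to be confirmed at two further site visits.
- Section 9.3 admits to the FAS only subjects with six weekly closure assessments or an earlier closure. Sections 9.4.1 to 9.4.3 run efficacy on the FAS and PP populations only.
- Section 9.4.7 leaves missing data to a separate SAP.

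**The concern.** A subject who misses two visits, or whose blinding is compromised, still has an ulcer that can be examined at week 12. Under Section 7.2 that examination is not made. A subject removed soon after first closure cannot supply the confirming visits. One removed early with an open ulcer leaves the primary analysis altogether. One removed after six assessments stays in the FAS, but the later outcome is unknown and the protocol has no rule for it.

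A later SAP can choose how to impute these outcomes; it cannot recover them. At stake is the validity of the randomised comparison. If removal is more frequent in one arm, or takes out subjects with a different prognosis in each arm, both exclusion and counting leavers as not closed can produce a difference where none exists. Uneven removal is plausible. Section 6.4 defines the compliance limits in terms of the IP, and the SoC arm has no gel. Section 6.3 relies on a shield to blind subjects, some of whom receive gel and some none. Section 10.1.8 leaves the grading of a violation as major to the Investigator's opinion.

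**Working it through.** **Inputs from Section 9.2.** Error rate and power: "To meet the Type I error rate of 0.05 (95% confidence interval), 2-sided analysis and 90% power". Closure rates: "39% of SoC vs 60% of Galnobax®-treated achieved complete closure of Target Ulcer". Allocation: "The randomization will be done at the ratio of 3:3:1 in one of the following groups", so 350 subjects split 150 : 150 : 50 and the efficacy comparison is 150 versus 150. Drop-out allowance: 20%.

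**The plan's own figure.** With pooled variance, p̄ = (0.60 + 0.39)/2 = 0.495:

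n = [1.960·√(2·0.495·0.505) + 1.282·√(0.60·0.40 + 0.39·0.61)]² / 0.21² = 117.03, so 118 per arm.

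The plan states 120, which agrees. Power at 120 per arm is 90.7% by this approximation and 90.0% by exact enumeration of the chi-square test. Inflation: 240/(1 − 0.20) = 300. This protects the number of evaluable subjects; it does not protect against selective removal.

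**Bias illustration.** Assumptions, not in the documents: true closure 39% in both arms, 150 randomised per arm, 25% removed from arm A and 15% from arm B. Rejection rate = Φ(d/se − 1.96) + Φ(−d/se − 1.96), with se = √[a(1−a)/n_A + b(1−b)/n_B].

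*Leavers counted as not closed* (n = 150 per arm): a = 0.39 × 0.75 = 0.2925; b = 0.39 × 0.85 = 0.3315; d = −0.039; se = 0.0535; rejection rate 11.3%.

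*Leavers excluded* (n = 112.5 and 127.5). If leavers would have closed at rate q, then a = (0.39 − 0.25q)/0.75 and b = (0.39 − 0.15q)/0.85:

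| q | a | b | d | Rejection rate |
|---|---|---|---|---|
| 20% | 0.453 | 0.424 | 0.030 | 7.5% |
| 10% | 0.487 | 0.441 | 0.045 | 10.9% |
| 0% | 0.520 | 0.459 | 0.061 | 15.8% |

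The two conventions err in opposite directions: the arm that loses more looks worse under the first and better under the second. With 20% removed from each arm and the same prognosis among leavers, d = 0 and the rate is 5% either way.

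**Does following everyone recover power?** Exact enumeration, two-sided 0.05, 150 per arm, assumed 20% leavers:

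| What happens to leavers | Galnobax rate | SoC rate | Power |
|---|---|---|---|
| Followed, close at 60% / 39% | 0.600 | 0.390 | 96.1% |
| Followed, close at 39% in both arms | 0.8·0.60 + 0.2·0.39 = 0.558 | 0.390 | 84.6% |
| Not followed, counted as not closed | 0.8·0.60 = 0.480 | 0.8·0.39 = 0.312 | 85.2% |

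With 10% leavers the last two rows become 91.8% and 91.9%. Follow-up restores power only to the extent that subjects off treatment keep the planned benefit, which nothing in the documents shows.

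**The case against.** **Section 7.1 already asks for more.** It wants as much relevant study information as possible on every discontinued subject, at a visit or by telephone. This is a fair point, but the request does not name closure, week 12 or the confirming visits. A telephone call cannot establish closure as judged by the blinded Investigator, and the same paragraph sets EOT/EOS back to the last visit.

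**Little is thrown away.** This stands. Closures confirmed before exit remain, and a subject with six weekly assessments stays in the FAS. The loss is of outcomes not collected.

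**Arm dependence.** A reader might infer that some triggers can occur only with gel. The documents do not establish that. Section 6.3 says "Unblinding will be done only if necessary for the welfare of the Subject or in the case of emergency suspected to be IP related"; a blinded Investigator could suspect the IP in an SoC subject, and subject welfare applies in any arm. Rule 6 in Section 7.2 speaks of treatment compliance without naming the IP, although Section 6.4 does name it. Uneven removal is plausible, not shown.

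**Power.** A reader might also infer that full follow-up lifts power from about 85% to 96%. That assumes leavers close at the full planned rates. It also attributes the whole 20% allowance to these rules, when the allowance must also cover withdrawn consent and loss to follow-up.

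**Some leavers cannot be assessed as planned.** Merged ulcers (rule 4) may not be traceable, and an Investigator whose own blinding is lost cannot give a blinded assessment. Both stand and limit the remedy.

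**Conclusion.** The point holds as a gap in outcome collection with a risk of bias. Section 7.2 ends participation for events that leave closure assessable, and the EOT/EOS wording with an AE-only follow-up list means later closure is not obtained.

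The size is conditional. Under an assumed 25% versus 15% removal and no true effect, the nominal 5% error rate becomes about 11% with leavers counted as not closed, or about 8% to 16% with leavers excluded and closing at 20% to 0%. With equal, prognosis-neutral removal it stays at 5%. The documents give no removal rates, so these figures show what could happen and do not predict it. No gain in power is claimed. The change should be made because outcomes not collected cannot be restored by the analysis.

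**What to change.** In Section 7.2, separate the end of study treatment from the end of study follow-up, leaving the events that end treatment unchanged. State that:

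- unless consent is withdrawn or the Target Ulcer can no longer be followed (for example, merged ulcers), blinded Target Ulcer assessments continue on the existing schedule to week 12, both closure-confirmation visits and End of Study;
- these outcomes enter the primary analysis whether or not six weekly visits were completed on treatment, with Section 9.3 worded to match;
- where the Investigator's own blinding is lost, the assessment is flagged and examined in a sensitivity analysis.

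Align the EOT/EOS wording in the notes to the Schedule of Activities (Section 1.3), Section 4.4 and Section 7.1, and add closure to the post-exit list in Section 7.2. That list's reference to End of Study also needs reconciling, because Section 4.4 ends the Study for a discontinued subject at the last recorded visit.

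The cost is a protocol amendment and some site effort to retain subjects who are off treatment. The visits used are already in the schedule; the documents give no budget, so the added expense cannot be stated.
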